7.3. Subject Randomization Criteria

Subjects must meet all of the following randomization inclusion criteria to be qualified to be randomized in this study:

1. Meets the following PANSS criteria at Visit 6 and Visit 8:
 - a. Has a total PANSS score between 50 and 80, inclusive
 - b. Has a score of ≤4 for all of the following PANSS Positive (P) Scale or General Psychopathology (G) items:
 - P1 (delusions)
 - P2 (conceptual disorganization)
 - P3 (hallucinatory behavior)
 - P6 (suspiciousness/ persecution)
 - P7 (hostility)
 - G8 (uncooperativeness)
2. Has a CGI-S score ≤4 at Visit 6 and Visit 8

Subjects must not meet any of the following randomization exclusion criteria to be qualified to be randomized in this study:

1. Has a positive drug screen for opiates (including buprenorphine, norbuprenorphine, codeine, hydrocodone, hydromorphone, methadone, morphine, oxycodone, and oxymorphone) at Visit 6

7.4. Subject Withdrawal

A completer is defined as any subject who completes the double-blind treatment period. A subject may be discontinued from the study at any time if the subject, PI, or Alkermes determines that it is not in the best interest of the subject to continue participation. Reasons for discontinuation include the following:

- AE
 - Note: An absolute neutrophil count $\leq 1.0 \times 10^3$ per μL anytime while on olanzapine should be cause for discontinuing a subject.
- Lack of efficacy
- Lost to follow-up
- Protocol violation (non-compliance with study drug or study procedures)
- Withdrawal by subject (eg, withdrawn consent)
- Pregnancy
- Study terminated by sponsor
- Other

If a subject withdraws from the study at any time for any reason, any ongoing AEs will be followed until resolution, until deemed stable by the PI, or until the subject is deemed by the investigator to be lost to follow-up. If, in the opinion of the PI or designee, it is necessary to monitor a subject beyond the safety follow-up visit, the follow-up period may be extended as necessary. In such instances, Alkermes and the PI will agree to an acceptable follow-up schedule.

In the event that a subject chooses to withdraw from the study, the PI should make a reasonable effort to ascertain the reason(s) for withdrawal, while fully respecting the subject's rights. The subject should be encouraged to return to the study center for an early termination (ET) visit, which will match the procedures at Visit 38 (see [Section 8](#)), and to complete a subsequent safety follow-up period. The safety follow-up period for subjects who discontinue early should mirror the safety follow-up visits displayed in [Table 3](#). If the subject fails or refuses to return to the study center, an attempt must be made to contact the subject by telephone in order to assess as many safety and efficacy parameters as possible. All data collected over the telephone must be documented and kept in the subject's record.

The investigator must maintain a record of all subjects who fail to complete the study. A full explanation of the reason for study discontinuation will be made on the appropriate electronic case report form (eCRF).

A subject will be deemed lost to follow-up after 3 attempts at contact have been made and it has been at least 1 month since the last subject contact. The 3rd attempt at contact must be a certified letter accompanied by a survey inquiring the reason for study discontinuation. All attempts at contact will be documented. The reason for discontinuation will be documented. If the PI becomes aware of a change in the subjects' status or receives more information about a subject's disposition, this information will be documented.

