Table 3: Schedule of Visits and Assessments for Continuation of Double-blind Treatment and Safety Follow-up Period (Visit 27-Visit 40)

	Double-blind Placebo-controlled Treatment												Safety Follow-up	
Study Visit	27	28	29	30	31	32	33	34	35	36	37	38/ ET	39	40
Study Week	41	43	45	47	49	51	53	55	57	59	61	63	41/ 65	42/ 66
Efficacy Measures														
PANSS ¹		X		X		X		X		X		X		X
CGI-S and CGI-I		X		X		X		X		X		X		X
TLFB ²		X		X		X		X		X		X		X
Cigarette Use Question						X						X		
VAS Desire for Alcohol		X		X		X		X		X		X		X
PSP		X						X				X		X
Exacerbation of Disease Criteria Review		X		X		X		X		X		X		
AIMS		X		X		X		X		X		X		X
SAS		X		X		X		X		X		X		X
BARS		X		X		X		X		X		X		X
Safety Assessments														
AE Monitoring		X		X		X		X		X		X	X	X
C-SSRS ³		X		X		X		X		X		X	X	X
Concomitant Medications		X		X		X		X		X		X	X	X
Medical History ⁴		X		X		X		X		X		X	X	X
Body Weight and Waist Circumference		X		X		X		X		X		X	X	X

Table 3: Schedule of Visits and Assessments for Continuation of Double-blind Treatment and Safety Follow-up Period (Visit 27-Visit 40) (Continued)

	Double-blind Placebo-controlled Treatment												Safety Follow-up	
Study Visit	27	28	29	30	31	32	33	34	35	36	37	38/ ET	39	40
Study Week	41	43	45	47	49	51	53	55	57	59	61	63	41/ 65	42/ 66
Brief Physical Exam		X						X						X
Vital Signs (including orthostatic measures)		X		X		X		X		X		X	X	X
Clinical labs ⁵		X						X				X		X
Electrocardiogram		X						X				X		X
Other Procedures														
Supportive Counseling		X		X		X		X		X		X		
Confirm Emergency Treatment Card		X		X		X		X		X		X	X	
Blood Samples for PK		X						X				X		X
Urine Drug Panel		X						X				X		
OL OLZ Dispensing	X	X	X	X	X	X	X	X	X	X	X	X	X	
DB S/P Dispensing	X	X	X	X	X	X	X	X	X	X	X			
Collect Emergency Treatment Card														X

Abbreviations: AE=Adverse Event; AIMS=Abnormal Involuntary Movement Scale; BARS=Barnes Akathisia Rating Scale; CDT=Carbohydrate deficient transferrin; CGI-I=Clinical Global Impression-Improvement; CGI-S=Clinical Global Impression-Severity; C-SSRS=Columbia Suicide Severity Rating Scale; DB=double-blind; ET=early termination; HbA_{1c}=Hemoglobin A1c; OL=open-label; OLZ=olanzapine; PANSS=Positive and Negative Syndrome Scale; PK=pharmacokinetics; PSP=Personal and Social Performance Scale; S/P=samidorphan/placebo; SAS=Simpson-Angus Scale; TLFB=Timeline Follow-Back; VAS=Visual Analog Scale

Shaded columns represent visits where only drug dispensing should occur.

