8.4. Study Requirements and Restrictions

8.4.1. Contraception and Pregnancy

All male and female subjects must agree to use an acceptable method of contraception for the duration of the study. At a minimum subjects must agree to use one of the following. Additional restrictions, if required, will be clarified in the locally-approved ICF or are clarified below.

- Double-barrier protection (eg, a condom with spermicide or a diaphragm with spermicide)
- Intrauterine device
- Oral contraceptive pills and other hormonal methods (eg, a vaginal ring, contraceptive patch, contraceptive implant); oral contraceptives must have been initiated at least 30 days prior to screening

Subjects must agree to use one of the following acceptable methods of contraception for the duration of the study:

- Condom (barrier method) plus
 - Intrauterine device
- or

- Hormonal contraceptive (such as birth control pills or patches, a vaginal ring, or a contraceptive implant); oral contraceptives must have been initiated at least 30 days prior to screening

Subjects who are abstinent are eligible to be in this study, provided they agree to use an acceptable contraceptive method should they become sexually active.

Subjects who are surgically sterile are exempt from the requirement to use contraception. Women who have undergone a hysterectomy, bilateral tubal ligation, or bilateral salpingo-oophorectomy are considered surgically sterile. Men who have undergone a vasectomy are considered surgically sterile. Partner vasectomy is not considered an approved acceptable method of contraception for a female subject.

Women who are postmenopausal are also exempt from the requirement to use contraception. For the purpose of this study, postmenopausal is defined as the permanent cessation of menstruation for at least 12 months prior to screening in women who are 45 years of age or older.

If any female subject becomes or is found to be pregnant while participating in the study, she will be discontinued from study drug immediately. The investigator must fill out a Pregnancy Report Form and submit the information to the sponsor within 24 hours of awareness of the pregnancy, irrespective of whether an adverse event has occurred. The early termination and safety follow-up visits will be scheduled.

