9. TREATMENT OF SUBJECTS

9.1. Study Drug Dose and Administration

Study drugs include samidorphan and matching placebo tablets, and olanzapine tablets, all for oral administration.

For all subjects, open-label samidorphan 10 mg will be taken once daily for 2 weeks prior to randomization. For subjects in the double-blind treatment period, samidorphan 10 mg (or placebo) will be taken once daily for up to 15 months.

For all subjects, the dose of olanzapine will be taken once daily (to be taken at the same time as samidorphan/placebo) at an individualized dose level. Olanzapine initiation, including transition from another antipsychotic (as applicable), is a highly individualized process. Formalizing the potential clinical scenarios may pose undue burden and/or risk to subjects. Clinical judgment is essential, and for this reason, the details of this process are left to the discretion of the treating physician, who will follow current clinical practice.

All subjects will be administered olanzapine for 11 to 17 months as part of this clinical trial.

ALKS 3831 should be taken as close to bedtime as possible. Subjects should not drive or operate heavy machinery until they know how ALKS 3831 will affect them.

After Visit 5, the dose level of olanzapine will be fixed, and an increase in dose level above the dose set at Visit 5 prior to randomization may cause the subject to be discontinued. The olanzapine dose level may be decreased at any time if the PI considers it medically beneficial to the subject, such as when a subject has stable psychiatric symptoms with side effects that may be reduced if the olanzapine dose level is decreased. If the PI decreases the dose level after randomization, only an increase above the dose level at randomization will be considered an EEDS.

At study drug dispensation visits, all subjects will receive blister cards containing samidorphan or placebo for self-administration; subjects will also receive olanzapine in separate packaging. Subjects will be instructed to take 1 tablet per day from the blister card in addition to their olanzapine tablet(s) once daily in the evening or at bedtime. The subject will take the final samidorphan/placebo dose the night before the final visit of the double-blind treatment period. Olanzapine dosing will continue uninterrupted through the end of the study. Any subject who prematurely discontinues from the study will be asked to return to the clinic for an ET visit and 2 safety follow-up visits.

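### Table 3 dispenses olanzapine at Visit 38/ET and Visit 39 without exception, which conflicts with the pregnancy stopping rule and leaves olanzapine unaddressed after a low-neutrophil discontinuation

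*Protocol*

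**What the plan says.** **Early termination and follow-up.** Section 7.4 gives the ET visit the content of Visit 38 ("early termination (ET) visit, which will match the procedures at Visit 38"). It adds: "The safety follow-up period for subjects who discontinue early should mirror the safety follow-up visits displayed in" Table 3. Section 8 sends prematurely discontinued subjects to Section 7.4. Section 9.1 asks any such subject to attend ET and two safety follow-up visits.

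**Dispensing.** The Table 3 row "OL OLZ Dispensing" is marked at Visit 38/ET and Visit 39. Section 8.3.27 ties dispensing to the visits marked in Tables 1 to 3. Section 9.1 lists olanzapine tablets among the study drugs and says: "Olanzapine dosing will continue uninterrupted through the end of the study".

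**Pregnancy.** Section 8.4.1 says of a subject found to be pregnant that "she will be discontinued from study drug immediately". The same paragraph schedules her ET and safety follow-up visits.

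**Neutrophils.** Section 7.4 says that an absolute neutrophil count of 1.0 x 10^3 per µL or less "anytime while on olanzapine should be cause for discontinuing a subject". Section 8.3.22 repeats this, allows a confirmatory test if an error is suspected, and otherwise discontinues the subject.

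**The concern.** The schedule treats the two components differently when the double-blind period ends. Samidorphan/placebo stops, and olanzapine is supplied again at Visit 38/ET and Visit 39. For a subject finishing as planned, that is coherent. The difficulty is that the same column serves early leavers, and some of them leave under rules that concern all study drug or that are triggered while on olanzapine. Nothing in the schedule separates those subjects from the rest.

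At stake is a study-drug instruction with direct patient-safety relevance. Staff dispensing from Table 3 and an investigator acting on Section 8.4.1 would do different things for the same pregnant subject, and each could cite the protocol. After a low-neutrophil discontinuation, the site has a dispensing mark but no statement of what is intended for olanzapine.

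**Working it through.** The documents state no figure to reproduce. The check is a count of marks in Table 3 followed by a comparison of passages.

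**Step 1: read the dispensing rows.** Table 3 has 14 visit columns: Visits 27 to 37 (11 columns), 38/ET, 39 and 40.

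| Row | Marks | Visits covered |
|---|---|---|
| Open-label olanzapine | 13 | 27 to 37 (11) + 38/ET (1) + 39 (1) = 13; blank at 40 |
| Double-blind samidorphan/placebo | 11 | 27 to 37 only |

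The table therefore separates the two drugs and keeps olanzapine going at ET and once more in follow-up.

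**Step 2: look for a condition.** The five numbered Table 3 footnotes cover the order of PANSS administration, who assists with the TLFB, the C-SSRS version, medical history and laboratory tests. None concerns olanzapine dispensing or the reason for leaving. Section 8.3.27 adds no exception.

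**Step 3: pregnancy.**

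- Section 8.4.1: study drug stops at once, then ET and follow-up visits are scheduled.
- Section 9.1: olanzapine is a study drug.
- Table 3 with Section 8.3.27: olanzapine is dispensed at Visit 38/ET and at Visit 39.

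A site that stops all study drug departs from the schedule. A site that follows the schedule departs from Section 8.4.1. The conflict does not depend on the ET sentence in Section 7.4, because Section 8.4.1 itself sends the subject to these visits.

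**Step 4: neutrophils.**

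- Sections 7.4 and 8.3.22: the subject is discontinued. Neither says that olanzapine stops or continues.
- Section 9.1: the subject is asked to attend ET and two follow-up visits.
- Table 3: olanzapine is marked at the first two of these three visits.

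A site can discontinue the subject and hold the visits without breaching either passage. The handling of olanzapine is left open.

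**Step 5: length of exposure.** Visit 38 is at week 63 and Visit 40 at week 66: 66 − 63 = 3 weeks. A subject on the 9-month schedule has the same interval, from Visit 26 at week 39 to Visit 40 at week 42: 42 − 39 = 3 weeks.

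**The case against.** The strongest reply is that the pregnancy rule is specific and urgent, whereas a schedule mark is general, so no site would resupply a subject already taken off study drug. Section 8.3.4 also requires immediate withdrawal on a positive test. Section 13.4 leaves therapeutic measures on withdrawal for an adverse event to the investigator, and Sections 8.4.5 and 9.4 make the PI responsible for trial-related medical decisions. This lowers the chance of harm. It does not remove the conflict, because general discretion does not tell a site which written instruction governs.

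A second reply concerns context in Section 9.1. The sentence on uninterrupted olanzapine follows directly on the one about the last samidorphan/placebo dose before the final double-blind visit, so it may be meant for completers. That is a fair reading and weakens the sentence as evidence. The pregnancy conflict still stands on Table 3, Section 8.3.27 and Section 8.4.1 alone.

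A reader might also draw stronger conclusions that the documents do not support:

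- **That every early leaver receives an ET visit and more olanzapine.** The Section 7.4 passage opens "In the event that a subject chooses to withdraw from the study" and continues "The subject should be encouraged to return to the study center for an early termination (ET) visit". Section 9.1 extends the visit to any premature discontinuation, but only as a request.
- **That the neutrophil rule is contradicted.** It discontinues the subject from the study and gives no express instruction to stop olanzapine.
- **That adverse events after discontinuation cannot be attributed.** Section 13.3 records relationship and action taken separately for olanzapine. Table 3 has PK samples at Visit 38/ET and Visit 40. SAP Section 3.8.1 ends double-blind treatment-emergent events at the last samidorphan/placebo dose and summarizes newly emergent events separately. Harm to attribution is not shown.

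**Conclusion.** The point holds in two parts of different strength. For a pregnant subject, Section 8.4.1 and the dispensing schedule conflict directly. This rests on reading study drug in Section 8.4.1 as Section 9.1 defines it, with olanzapine included. For a subject discontinued for a low neutrophil count, the documents leave the handling of olanzapine unstated while the schedule still dispenses it.

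The size is up to 3 weeks of olanzapine per affected subject, from two dispensing visits, provided the subject attends. The documents give no count of affected subjects and no rate from which to derive one, so none is offered. The primary efficacy analysis is not in question. The issue is a conflict between study-drug instructions that matters for patient safety and is cheap to remove.

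**What to change.** Reconcile the olanzapine row of Table 3 at Visit 38/ET and Visit 39 with Sections 7.4, 8.3.22, 8.3.27, 8.4.1 and 9.1, so that all state one consistent rule for olanzapine at and after early termination. The text should cover pregnancy and low-neutrophil discontinuation explicitly, and should make clear whether the continuation sentence in Section 9.1 applies to early leavers. The rule should be visible in Table 3 or its footnotes as well as in the body, since sites dispense from the table. Which rule applies, and which passage changes, is the sponsor's medical decision and is not proposed here.

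The cost is a few wording changes in a protocol amendment, with no additional visits, assessments or data.

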7.5. Replacement of Subjects

Subjects who are discontinued or lost to follow-up after randomization will not be replaced.

7.6. Identification of Informant or Caregiver

In some cases a caregiver may be required for a subject to join the study (eg, by a local institutional review board [IRB] or independent ethics committee [IEC]). As per inclusion/exclusion criteria, subjects in Bulgaria are required to have an informant or caregiver who meets the following criteria:

- a. Informant or caregiver will be in contact with the subject several times per week.
- b. If necessary, the informant or caregiver will accompany the subject to visits.
- c. Informant or caregiver will help ensure maximum subject adherence to study procedures.

In all other cases, an informant or caregiver (hereafter, caregiver) should be identified whenever possible. This person should be in contact with the subject and be able to help with adherence to study procedures (including attending study visits when needed).

7.7. Withdrawal and Replacement of Informant or Caregiver

Some sites may require the caregiver to sign a caregiver ICF (separate from a subject ICF). A caregiver who is required to sign a caregiver ICF may withdraw consent at any time, in which case he/she can no longer fill the caregiver role for this study. Any other caregiver may decide to stop cooperating with study staff or be lost to follow-up, in which case he/she can no longer fill the caregiver role for this study. If a caregiver can no longer fill the caregiver role, he/she should be replaced if possible. If the caregiver cannot be replaced, most subjects will be able to continue in the study. In Bulgaria, the caregiver must be replaced in order for the subject to continue in the study. If the subject must also withdraw from the study (eg, the subject is in Bulgaria, and no alternative caregiver is available or the caregiver provided transportation to the site and no other travel arrangements can be made for the subject), the PI should make a reasonable effort to ascertain the reason(s) for the caregiver's withdrawal, while fully respecting the caregiver's and subject's rights.

8. STUDY DESIGN

[figure not shown]
This is a Phase 2, multicenter, randomized, double-blind, placebo-controlled study designed to evaluate the efficacy, safety, and tolerability of ALKS 3831 in schizophrenia with AUD. Subjects experiencing disease symptom exacerbation (eg, inpatient hospitalization) within the past 6 months will be considered for screening. Assessment of eligibility is based on DSM-IV-TR diagnosis of schizophrenia and DSM-5 diagnosis of AUD (supported by the subject's medical history, subject self-report, and caregiver or informant report of medical history and/or drinking behavior and confirmed via the MINI and C-VISA). Subjects must also meet certain clinical criteria at screening and prior to randomization. These criteria include (but are not limited to) having a PANSS score between 50 and 90 (inclusive) at screening and Visit 2 and between 50 and 80 (inclusive) at Visit 6 and Visit 8; a PANSS item score of ≤ 4 on Positive (P) Scale and General Psychopathology (G) items P1, P2, P3, P6, P7, and G8; and a CGI-S score ≤ 4 at screening, Visit 2, Visit 6, and Visit 8. Subjects who do not meet PANSS or CGI-S criteria at screening but were prescribed olanzapine during a recent hospitalization (discharged within the 2 weeks prior to screening) may be eligible for the study if they meet symptom severity criteria at Visit 2, Visit 6, and Visit 8. Other eligibility criteria assessed between screening and randomization are ECG (Visit 2) and drug screening (Visit 6) criteria. Complete eligibility criteria are given in [Section 7.1](#) and [Section 7.2](#), and randomization criteria are given in [Section 7.3](#).

All study visits will be outpatient visits. The olanzapine dose level throughout the study will be determined individually by the PI according to current clinical practice.

Subjects who are taking an antipsychotic other than olanzapine or no antipsychotic medication at Visit 2 will be tapered off of current medication (if applicable) and titrated onto olanzapine beginning at Visit 2 (see [Figure 1](#)) according to a schedule determined by the investigator in accordance with current clinical practice. Subjects who are already taking olanzapine will take their medication as currently prescribed at Visit 2 and for a period of 4 weeks (Visits 3–5) prior to initiation of ALKS 3831 (Visit 6). After Visit 2, all subjects will return to the clinic weekly for dose adjustment, as necessary (permitted at Visits 3 and 4 only), and safety monitoring (Visits 3–5). A cross-taper period of up to 3 weeks is expected when switching to olanzapine and optimizing olanzapine dose.

Unless a change in olanzapine dose is medically indicated, it will remain fixed for the remainder of the study after Visit 5. An increase in dose between Visit 5 and randomization may be a reason for withdrawal from the study, and an increase in dose after randomization is considered an EEDS (see [Section 11.1](#)). A decrease in dose is always allowed when medically indicated. If a dose reduction occurs after randomization, any subsequent dose must be greater than the dose at randomization for this increase to be considered an EEDS.

Figure 1: ALK3831-401 Study Schematic

Abbreviation: V = Study Visit; ALKS 3831=olanzapine plus samidorphan

At Visit 6, subjects will begin a 2-week open-label ALKS 3831 (olanzapine [fixed-dose] coadministered with samidorphan [10 mg]) treatment period. Subjects who do not tolerate ALKS 3831 during this open-label period may be discontinued from the study prior to randomization.

At Visit 8, subjects will be randomized in a 1:1 fashion to 1 of 2 treatment groups and will begin a double-blind treatment period. The 2 treatment groups are as follows:

- ALKS 3831: (ie, olanzapine [dose determined by the PI] plus samidorphan [10 mg])
- Olanzapine (dose determined by the PI) plus placebo

During the double-blind treatment period, subjects will complete an outpatient visit every 2 weeks. As indicated in the schedule of assessments (see [Table 1](#), [Table 2](#), and [Table 3](#)), at some of these visits, subjects will complete a number of clinical assessments, receive a 15-minute counseling intervention (see [Section 8.3.26](#)), and will receive a 2-week study drug supply (including extra medication in case the subject does not return to the study site on the scheduled day; see [Section 10](#)). Other visits will be only drug dispensing visits during which subjects will only receive a 2-week study drug supply. No clinical assessments will be completed at drug dispensing visits.

Subjects randomized to double-blind treatment will be followed for a minimum of 9 months and a maximum of 15 months. After the end of the double-blind treatment period, subjects will complete a 3-week safety follow-up period. The study will be stopped when the last subject randomized is scheduled to complete Visit 26. When the last subject is randomized, all subjects currently participating in the study will be informed of the target completion date of the study period. After the last double-blind treatment period visit, subjects will proceed to the safety follow-up period.

The duration of the double-blind period will be between 9 and 15 months, depending on when the study is stopped. The target completion date will be based on the number of subjects randomized with enrollment ending when approximately 270 subjects have been randomized. After the last subject is randomized, the end date of the study will be set to occur approximately 9 months later and subjects will be informed of the target completion date. Final

samidorphan/placebo dosing for these subjects will take place the night before their final visit of the double-blind treatment period. A subject who is prematurely discontinued from the study will proceed as described in [Section 7.4](#).

After a subject completes an ET Visit and/or the safety-follow-up period, follow-up clinical care may be provided for up to 3 months if the PI determines that it is medically indicated. This care may include payments for medication and up to 3 clinic (outpatient) visits.

